### **ACR20/50/70 response rates at all assessment points**

The number and proportion of ACR20, ACR50 and ACR70 responders will be summarised for each randomised treatment group and visit. Fisher's exact test will be used to test for randomised treatment group differences in the proportion of ACR20/50/70 responders at all assessment points for each GSK3196165 treatment group versus placebo.

#### **4.9.2.2 Week 24 Analysis and Final Analysis**

The goal of the Week 24 analysis is to provide unblinded results for all endpoints that are evaluable at this timepoint except actigraphy. The Final analysis will include all analyses and endpoints.

For the Week 24 analysis, tabular summaries of efficacy data will be provided at all visits through Week 62 where available. Graphical presentations for efficacy endpoints will include data through the Week 24 visit. Statistical analyses will also include data through the Week 24 visit. All safety data collected at the time of the Week 24 data cut will be summarised. See section [4.9](#) for a description of safety summaries.

The following table indicates the types of summaries and analyses that will be conducted for each primary and secondary efficacy endpoint.

**Table 6 Summaries and Analyses for Primary and Secondary Endpoints**

	Summary Statistics						Statistical Analyses							
	Observed	CfB/Proportion			Subgroups	Dose Response			MMRM/Logistic			Survival (Time to 1st)		
	T	T	F	L	T	T	F	O	T	F	O	T	F	O
DAS28(CRP) score	Y	Y	Y	Y	Y1	Y at Week 24	Y	Y	Y	Y	Y			
DAS28(CRP) remission		Y		Y	Y1	Optional at Week 24	Y	Y	Y		Y	Y	Y	Y
DAS28(CRP) EULAR response		Y		Y	Y1				Y		Y			
ACR20/50/70		Y		Y	Y1				Y		Y			
Components: TJC28, TJC68, SJC28, SJC66, CRP, PtGA, PhGA	Y	Y		Y					Y		Y			
Index- and Boolean-based ACR/EULAR remission		Y			Y1				Y		Y			
CDAI remission		Y							Y		Y			
SDAI, CDAI scores	Y	Y							Y	Y	Y			
HAQ-DI score	Y	Y							Y	Y	Y			
HAQ-DI pain severity				Y										
Pain score	Y	Y							Y	Y	Y			
SF-36 physical, mental and domain scores	Y	Y							Y	Y	Y			
FACIT-Fatigue	Y	Y		Y					Y	Y	Y			
BFI Question 3	Y	Y		Y					Y	Y	Y			

CfB=Change from baseline; T=table; F=figure; L=listing; O=supportive analysis SAS output.  
1 Disease duration ((<2 years,  $\geq$ 2 years), gender.

For plots of change from baseline endpoints, the mean change from baseline and 95% CI will be plotted by randomised treatment group.

Plots of Mean and 95% CI of Change from Baseline in DAS28(CRP) at Each Visit will be created.

Subject profile plots of DAS28 score at each visit will be produced.

Dose response analyses for change from baseline in DAS28(CRP) will be conducted after visual inspection of the mean and 95% CI plots and using the final model from the second interim analysis as a starting point for the dose response modelling. The Week 24 primary analysis model will be fitted without covariate terms. A plot of the residuals versus predicted values will be examined to assess distributional assumptions. If additional models are fit, the smallest AIC will be used to help identify the best fitting model. Covariates from the Week 24 primary analysis of DAS28(CRP) remission may be added to the model in a sensitivity analysis. Model results from the sensitivity analysis will be provided in the corresponding listing.

Dose response analyses for DAS28(CRP) remission might be done as an ad-hoc analysis. MMRM analyses will be conducted similarly to interim analysis methods. Distributional assumptions underlying the model used for analysis will be examined by obtaining a normal probability plot of the residuals and a plot of the residuals versus the predicted values (i.e. checking the normality assumption and constant variance assumption of the model respectively) to gain confidence that the model assumptions are reasonable. If there are any departures from the distributional assumptions, alternative models may be explored using appropriate transformed data

For change from baseline in DAS28(CRP), if the dropout rate is  $\geq 10\%$  for the Week 24 or Week 52 analysis, further sensitivity analyses using multiple imputation as explained in section 4.5.2.3 may be conducted as ad-hoc analyses. In order to assess subgroup effects, additional analyses will be conducted with subgroup and subgroup interaction with treatment as covariates.

For DAS28(CRP) remission, subjects with missing data as defined in Section 3.2.1 will be imputed as non-responders as described in Section 4.5.2.1. Differences in remission rates between each active arm and placebo will be summarised at each visit through Week 52. 95% CI for the differences will be constructed using their asymptotic standard errors (asymptotic Wald confidence limits) without continuity correction.

Logistic regression models will have fixed effects for randomised treatment group and baseline value. The odds ratios, 95% CI and p-values for the comparison of each GSK3196165 treatment group versus placebo at key time points will be presented. Covariates age, gender, weight and disease duration ( $<2$  years,  $\geq 2$  years) will be considered in alignment with the results of the primary analysis model.

For ACR response, baseline values of TJC68 and SJC66 will be considered as fixed effects, as a baseline value of ACR response does not exist.

For binary endpoints with repeated measures over time, Generalized Estimating Equations (GEE) methodology will be used to take correlation among subject-level responses over time into account. The model will include data from all assessment points from Week 1 to Week 62. Due to only few expected subjects with remission in some randomised treatment groups (especially placebo) only standard errors and resulting confidence intervals will be adjusted. To this end an independent working correlation structure will be assumed and standard errors will be calculated based on the empirical sandwich covariance estimate (default setting for PROC GENMOD in SAS) (Stokes, Davis, & Koch, 2012).

For the primary analysis of DAS28(CRP) remission at Week 24, the GEE model will include terms for randomised treatment group, baseline DAS28(CRP), visit and interaction terms for treatment group-by-visit and baseline-by-visit. A sensitivity analysis including covariates age, gender, weight and disease duration (<2 years,  $\geq 2$  years) will be considered by adding covariate terms to the repeated measures model one at a time along with the covariate-by-treatment group interaction term. If the interaction term is not significant at  $\alpha=0.10$  it will be removed from the model. Likewise, if the covariate term is not significant at  $\alpha=0.10$  it will be removed from the model. Other covariates will be tested in a similar manner.

Survival analyses (time to event analyses) will be conducted for the final analysis using Kaplan-Meier methods, comparing each GSK3196165 dose to placebo. Between-group differences will be analysed using the log-rank statistic. Median time to remission will be presented for each randomised treatment group. Kaplan-Meier plots of the time to remission will be presented. Subjects who withdraw from the study are censored at the time of withdrawal. All other subjects are censored at the end of the study.

In addition to summaries of the individual components of composite endpoints, numbers and percentages of subjects meeting the following criteria will be presented:

- TJC68  $\leq 1$
- SJC66  $\leq 1$
- CRP  $\leq 1\text{mg/dl}$
- PtGA  $\leq 10$
- SDAI  $\leq 3.3$

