#### 9.2.1.2. Dose Response Analysis

It is estimated the dose response analysis can be conducted once a minimum of 15 subjects in each of the six treatment groups complete 12 weeks of treatment. Other analyses at earlier time points may also be conducted. The sample size has been estimated using simulation.

The anticipated dose response curve assuming the numbers summarised below, and the precision around it was obtained through 100000 simulations where the following changes from baseline in DAS28(CRP) have been assumed at each dose level, with a between subject standard deviation of 1 (based on Phase 2 data in a DMARD-IR population):

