## 9.3. Data Analysis Considerations

### 9.3.1. Analysis Populations

**Intent to Treat (ITT) population:** The ITT population is defined as all subjects who were randomised to treatment and who received at least one dose of study treatment.

**Pharmacokinetic (PK) population:** The PK population is defined as all subjects who were randomised to treatment, who received at least one dose of study treatment and who have at least one valid pharmacokinetic assessment.

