### **9.4.2. Secondary Analyses**

The key secondary analysis of assessing dose response at 12 weeks will be based on the change from baseline in the DAS28(CRP) continuous score after 12 weeks of treatment. Primary inference will be based on the ITT population, as defined in Section 9.3.1 and the analysis will be performed using the OC dataset. Further sensitivity analyses using multiple imputation may be conducted if the rate of dropout is larger than expected (<10% to Week 12).

It is expected that the shape of the dose response curve will be sigmoidal and the data will be initially analyzed using a three parameter  $E_{max}$  model of the form:

$$Y = E_0 + E_{max} * [Di / \{ ED_{50} + Di \}]$$

where  $E_0$  is the minimum dose effect or placebo effect,  $E_{max}$  is the maximum achievable effect above placebo,  $ED_{50}$  is the dose at half  $E_{max}$  and  $Di$  are doses =0, 22.5, 45, 90, 135 and 180 mg.  $Y$  is a measure of DAS28(CRP) continuous score.

If this  $E_{max}$  model is not applicable then additional models will be investigated, including a four parameter  $E_{max}$  model and the model with the expected response as a linear function of dose. These models will be detailed in the reporting and analysis plan (RAP), along with further details of the analyses to be conducted. Each of the models will be fitted to the data and their fit compared using the Aikake information criteria (AIC), where the model with the lowest AIC will be the primary model for inference. The additional models will be considered secondary models, and will not be utilised unless issues arise with the residual checks on the primary model.

Distributional assumptions underlying this analysis will be assessed (further details will be included in the RAP).

All binary secondary endpoints will be analyzed using the same methods as for the primary endpoint. Continuous secondary endpoints, apart from the assessment of dose response, will be analyzed using a repeated measures model (MMRM). Further sensitivity analyses may be conducted using multiple imputation if the rates of dropout are high. Full details will be given in the RAP.

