#### **4.5.2.3 Multiple Imputation: Predictive Mean Matching**

For further sensitivity analyses for DAS28(CRP), multiple imputation may be conducted (see section [4.9.2](#)). If needed, this will be conducted as an ad-hoc analysis by GSK.

The multiple imputation procedure will assume that the observed visit data are from a multivariate normal distribution and that data are missing at random. Depending on the missing data pattern, either the predicted mean matching method (monotone missing pattern) or the MCMC method (either monotone or non-monotone missing pattern) for imputation will be used.

The sensitivity analysis will follow steps 1 to 3:

1. Using PROC MI, missing data will be filled in  $m$  times to generate  $m$  complete datasets using the observed data. If the MCMC method is used, specify IMPUTE=FULL to impute all missing values.

2. Change from baseline will be calculated in each of the  $m$  complete datasets and then analyzed using the appropriate dose response model identified at the second interim analysis.
3. Using PROC MIANALYZE, the  $m$  sets of estimated parameters from the dose response model will be combined to form the mean and standard deviation of each parameter for use in inference regarding the dose response relationship at Weeks 24 or 52 visits.

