#### Dose response relationship (change from baseline in DAS28(CRP) at Week 12):

The null hypothesis (H0) for the dose response relationship assumes that there is no effect of the test drug and hence no evidence of a dose response relationship with respect to the change from baseline in the DAS28(CRP) continuous score. This is equivalent to saying that none of the active doses differs from placebo:

H0: Placebo = 22.5 mg = 45 mg = 90 mg = 135 mg = 180 mg

Whereas the alternate hypothesis (H1) assumes that there is a significant relationship between GSK3196165 dose and response with respect to the change from baseline in the DAS28(CRP) continuous score. It is expected that this relationship will follow an Emax model or more generally is a monotone relationship:

H1: Placebo  $\geq$ 22.5 mg  $\geq$ 45 mg  $\geq$ 90 mg  $\geq$ 135 mg  $\geq$ 180 mg

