#### **4.9.1.2 Multi-center Studies**

This study will randomise 210 subjects into 6 treatment arms, so that on average only 35 subjects per arm will be enrolled (although some arms may have larger patient numbers if inferior arms are dropped at the interim analyses). The number of sites (centres) may be roughly around 70, so that an adjustment of the analyses by centre will not be feasible.

For all analyses all sites, countries and regions will be pooled.

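### The SAP explicitly schedules the Week 12 dose-response model, the protocol's key secondary analysis, only at the interims; its Week 24 and final section names Week 24 instead

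*SAP*

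**What the plan says.** Protocol section 9.4.2 states: "The key secondary analysis of assessing dose response at 12 weeks will be based on the change from baseline in the DAS28(CRP) continuous score". It continues: "Primary inference will be based on the ITT population, as defined in Section 9.3.1". Section 9.3.1 defines that population as "all subjects who were randomised to treatment and who received at least one dose of study treatment". SAP section 4.9.1.2 gives the planned size: "This study will randomise 210 subjects into 6 treatment arms". SAP section 4.9.1.1 keeps the hypothesis at the same visit, under the heading "Dose response relationship (change from baseline in DAS28(CRP) at Week 12".

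The SAP describes Week 12 dose-response modelling in section 4.9.2.1 (Interim Analyses). Table 5 lists it as an interim output, the method text there gives the Emax form for Weeks 4, 8 and 12, and Table 4 sets the second interim at 90 subjects completing Week 12.

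Section 4.9.2.2 covers the Week 24 and final analyses. In Table 6 the dose-response entry for the DAS28(CRP) score is qualified by Week 24. The text below it says the analysis is done "using the final model from the second interim analysis as a starting point for the dose response modelling" and names no Week 12 fit. Step 3 of the optional multiple imputation in section 4.5.2.3 is for "inference regarding the dose response relationship at Weeks 24 or 52 visits". Section 4.14, which lists departures from the protocol, does not mention the visit for dose response.

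**The concern.** The study exists to choose doses for Phase 3, and the protocol places the dose-response question at Week 12, the last scheduled assessment before any subject can change dose. If a programmer follows section 4.9.2.2 literally, the Emax model in the unblinded reports is fitted at Week 24, and the only Week 12 Emax fit is the one the DRC saw on about 90 subjects.

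Two things are at stake. One is precision, since 120 of the 210 planned subjects would not enter any explicitly scheduled Week 12 dose-response fit. The other is comparability of the arms: by Week 24 the poorest responders in every arm except 180 mg have been removed from the continuous analysis. If the visit is settled only after unblinding, the choice could also look data-driven.

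**Working it through.** **1. Where each document puts the model**

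- Protocol 9.4.2: Week 12, ITT, key secondary.
- SAP 4.9.1.1: hypothesis at Week 12.
- SAP 4.9.2.1, Tables 4 and 5: Week 12 model at the interims, about 90 subjects.
- SAP 4.9.2.2, Table 6: dose response marked for Week 24; Week 12 not named.
- SAP 4.5.2.3, step 3: Weeks 24 or 52; Week 12 not named.
- Imputation trigger: dropout to Week 12 in protocol 9.4.2; dropout for the Week 24 or Week 52 analysis in SAP 4.9.2.2.
- SAP 4.14: no change declared.

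**2. Reproducing the plan's own curve**

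Protocol section 9.2.1.2 gives E0 = -1.0, Emax = -1.65 and SD = 1, but no ED50. Taking ED50 = 45 mg in E0 + Emax × D/(ED50 + D):

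- 22.5 mg: -1 - 1.65 × 1/3 = -1.55 (Table 3: -1.54)
- 45 mg: -1 - 1.65 × 1/2 = -1.83 (-1.83)
- 90 mg: -1 - 1.65 × 2/3 = -2.10 (-2.1)
- 135 mg: -1 - 1.65 × 3/4 = -2.24 (-2.24)
- 180 mg: -1 - 1.65 × 4/5 = -2.32 (-2.32)

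So an ED50 of about 45 mg is inferred from the plan, not stated in it. Simulating this model by least squares at 20 per arm and SD 1 gives 2.5 and 97.5 percentiles of -2.68 and -2.02 at 180 mg (protocol Table 7: -2.69 and -1.99) and -1.42 and -0.57 at placebo (-1.44 and -0.49). This is close enough to use. The precision percentages in protocol Table 4 reproduce only in part. The documents do not define precision; reading it as a 95% half-width below 0.45 gives 90.7% at 22.5 mg (stated 90.4%) and 100% at 135 mg (98.9%), but 88 to 91% at 180 mg (95%).

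**3. Precision at 15 and 35 per arm**

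SD of the fitted 180 mg minus placebo difference, same model:

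- 15 per arm (90 subjects): about 0.30, so 1.96 × 0.30 = 0.59
- 35 per arm (210 subjects): about 0.20, so 1.96 × 0.20 = 0.39

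The ratio agrees with sample size alone: √(210/90) = 1.53.

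**4. Why Week 24 is a different question**

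Under SAP section 4.5.2.1, subjects rescued at Week 14 have continuous values set to missing from that visit on. Rescue follows EULAR non-response at Week 12. In SAP Table 2, improvement of 0.6 or less is always non-response; improvement above 0.6 and up to 1.2 is non-response only if the current score exceeds 5.1. The non-response rate therefore lies between P(improvement ≤ 0.6) and P(improvement ≤ 1.2). With Table 3 means, SD 1 and normality:

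- Placebo: 1 - Φ(0.4) = 34% to 1 - Φ(-0.2) = 58%
- 22.5 mg: 1 - Φ(0.94) = 17% to 1 - Φ(0.34) = 37%
- 135 mg: 1 - Φ(1.64) = 5% to 1 - Φ(1.04) = 15%
- 180 mg: none, because there is no higher dose to move to

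For illustration, let each subject's Week 24 change equal the Week 12 change. For threshold c, the mean among those remaining is μ - φ(c - μ)/Φ(c - μ). With c = -0.6 and -1.2:

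- Placebo moves from -1.0 to -1.56 or -1.93.
- 135 mg moves from -2.24 to -2.35 or -2.51.
- 135 mg minus placebo moves from -1.24 to -2.35 + 1.56 = -0.79, or -2.51 + 1.93 = -0.58.

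The curve flattens through selection alone.

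**The case against.** No sentence confines Week 12 modelling to the interims. Week 24 is also the name of a delivery in SAP Table 4, so the Table 6 entry may mean output produced at that delivery. Section 4.9.2.2 says the Week 24 analysis covers every endpoint evaluable by then and the final analysis covers everything, and Week 12 change is a listed endpoint. Fitting the model early is also no departure: protocol section 9.2.1.2 says the analysis "can be conducted once a minimum of 15 subjects in each of the six treatment groups complete 12 weeks of treatment", and the interim outputs are themselves labelled ITT. All of this stands, and it is why the gap is one of explicit scheduling. Against it, section 4.5.2.3 refers to visits, not deliveries, and omits Week 12, although it describes only an optional sensitivity analysis. A minimum for an early fit is also not a cap.

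A reader might infer that the trial would report no Week 12 result on its full population, or that 57% of the Week 12 data (120/210) go unused. The documents do not support either. Section 4.9.2.2 and Table 6 require DAS28(CRP) summaries, plots of mean change at each visit and an MMRM, and all subjects' Week 12 data enter these. They give dose-group estimates, though not the dose-response model the protocol names. Nor do the documents show that the full Week 12 fit was deliberately dropped: silence in section 4.14 is equally consistent with an oversight.

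This is also a Phase 2b study without multiplicity control, and the data are collected in any case. That limits how serious the gap is.

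**Conclusion.** The concern holds as a should-fix. The key secondary model is explicitly scheduled only on about 90 subjects, and the section governing the Week 24 and final reports points to a visit where selective removal of escaped subjects changes the comparison.

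The gain from the full fit is a fall in the SD of the 180 mg minus placebo estimate from about 0.30 to about 0.20. That rests on an inferred ED50 of about 45 mg, SD 1 and all six arms reaching 35. The plan allows arms to be dropped and later subjects reallocated, which would change the figures. The Week 24 attenuation is an illustration under normality and unchanged scores after Week 12; its direction is more secure than its size.

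**What to change.** In SAP section 4.9.2.2 and Table 6, state that the Week 12 dose-response model for change from baseline in DAS28(CRP) is fitted on all ITT subjects at the Week 24 analysis as the key secondary analysis, alongside the Week 24 fit. Add Week 12 to step 3 of section 4.5.2.3.

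If the move to Week 24 was intended, declare and justify it in section 4.14. Either way, settle it before the Week 24 unblinding. The cost is SAP wording and one more model run; no new data are needed.

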### 3.1.3 Treatment Arms and Duration

In the “dose selection” component of the study, subjects will be randomised (1:1:1:1:1) to placebo or one of five subcutaneous GSK3196165 doses, in combination with MTX (at a dose between 15-25 mg previously received for at least 12 weeks, with a stable and tolerated dose and route of administration for  $\geq 4$  weeks).

Treatment with GSK3196165 will be given as a single subcutaneous (SC) injection by an unblinded administrator (shielded to subjects) weekly for 5 injections (Days 1, 8, 15, 22, 29), then EOW thereafter beginning at Day 43 (Week 6).

GSK3196165/placebo must be administered on the same day each week  $\pm 1$  day for the first 5 weekly doses. Following this GSK3196165/placebo must be administered on the same day EOW  $\pm 3$  days.

After the Day 85 (Week 12) administration:

- “Escape therapy” is provided for all subjects not on the 180 mg dose:
  - Subjects in the placebo, 22.5 mg, 45 mg, 90 mg and 135 mg arms will be escalated in a double-blind fashion to the 180 mg (or the highest remaining) dose at Week 14 if they have failed to achieve European League against Rheumatism (EULAR) good/moderate response (see section 3.2.1) at Week 12.
  - Subjects in these groups who do not meet this criterion and therefore do not escalate therapy at Week 14 have another opportunity for “escape” at Week 24 with escalation in a double-blind fashion to the 180 mg (or the highest remaining) dose at Week 26 if their DAS28(CRP) score at this timepoint is  $>3.2$ .

This escape requirement is based on EULAR guidance and a review of response to MTX in randomised clinical studies.

Any subject that does not achieve EULAR good/moderate response at Week 36 will not be dosed at Week 38, and will be withdrawn from the study.

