#### 4.3.1 Analysis Datasets

For each of the efficacy evaluations of binary endpoints, subjects with missing efficacy data, early withdrawals, subjects who received more than 10 mg/day of prednisone equivalent oral corticosteroids, subjects with any new use of parenteral corticosteroids, more than one intra-articular corticosteroid injection within a 24 week period, or subjects who received rescue treatment will be imputed as non-responders and therefore treated as a failure (e.g. no DAS28(CRP) remission or no moderate/good EULAR response). Imputation rules for each case are described in section 4.5.2:

A dataset will be created with these imputation rules and will be referred to as the NRI dataset. The NRI dataset will be the primary dataset used for all binary efficacy endpoints. Imputed response for each binary endpoint will be presented by visit and subject in listings.

For the efficacy evaluations of continuous endpoints, results recorded for subjects who received rescue treatment or exceeded 10 mg/day prednisone equivalent oral corticosteroids, subjects with any new use of parenteral corticosteroids, more than one intra-articular corticosteroid injection within a 24 week period, or subjects who received rescue treatment will be set to missing at the same visits that were set to non-responder for the binary endpoints. This is a change from protocol section 9.3.2. A dataset will be created and will be referred to as the Set-to-Missing (STM) dataset.

For safety endpoints, no imputation for missing data will be done.

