## 4.5.2 Missing Data for Efficacy and Safety Endpoints

### 4.5.2.1 Missing Data for Efficacy Endpoints

Missing visit data for each efficacy endpoint will be handled as described in Sections 3.2 and 4.3.1. For each continuous endpoint, change from baseline will be missing at visits with missing post-baseline values or where data were imputed to missing.

For the binary endpoints, subjects with missing efficacy data, early withdrawals, subjects who exceed the allowed dose of corticosteroid, who received new parenteral corticosteroids or more than one intra-articular corticosteroid injection within a 24 week period, or subjects who received rescue treatment will be imputed as non-responders and therefore treated as a failure (e.g. no DAS28(CRP) remission or no moderate/good EULAR response).

For subjects who exceed the allowed dose of corticosteroid, who received new parenteral corticosteroids or more than one intra-articular corticosteroid injection within 24 weeks or subjects who received rescue treatment, continuous efficacy endpoints will be set to missing.

- Missing efficacy data: visits with missing data (due to a missed visit or missing component of a composite endpoint) should be set to treatment failure.
- Early withdrawals (including subjects that are withdrawn at Week 36 due to lack of EULAR response): only visits following the early withdrawal visit should be set to treatment failure.
- Prednisone equivalent >10 mg/day: the visit after a period (time from previous visit up to the day before the current visit) of average daily corticosteroid use exceeding 10 mg/day prednisone and all following visits should be set to treatment failure (continuous endpoints will be set to missing).
- Parenteral corticosteroids: all visits after a subject received any new parenteral corticosteroids (e.g. intravenous and intra-muscular) should be set to treatment failure (continuous endpoints will be set to missing).
- Intra-articular corticosteroids: all visits after the second intra-articular corticosteroid injection within a 24 week period should be set to treatment failure (continuous endpoints will be set to missing).
- Rescue: subjects who rescue to 180 mg dose at Week 14 or 26 should be set to treatment failure at that visit and all subsequent visits (continuous endpoints will be set to missing).

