**Table 5 List of Outputs for Interim Analyses (IA)**

Endpoint	Output	IA1	IA2	Produced by
n/a	Summary of Demography Characteristics – Disease History	Y	Y	PAREXEL 
DAS28(CRP) change from baseline	Summary of the Change from Baseline in DAS28(CRP) at Each Visit	Y	Y	GSK
	Plot of Mean and 95% CI of Change from Baseline in DAS28(CRP) by Visit and Randomised Treatment Group (1 plot)	Y	Y	GSK
	Plot of Mean and 95% CI of Change from Baseline in DAS28(CRP) Across Doses at Weeks 4, 8 and 12 (3 plots)	Y	Y	GSK
	Mixed Model Repeated Measures Analysis (MMRM) of Change from Baseline in DAS28(CRP) Through Week 12	Y	Y	GSK
	Plot of Least Squares Means and 95% CI of Change from Baseline in DAS28(CRP) (from MMRM)	Y	Y	GSK
	Dose Response Modelling of Change from Baseline in DAS28(CRP) at Weeks 4, 8 and 12	Y	Y	GSK
	Plot of Dose Response Model at Weeks 4, 8 and 12	Y	Y	GSK
DAS28(CRP) remission	Posterior Probability of the Difference in the Change from Baseline over Placebo < -1.0 at Week 12 for Each Dose	Y	N	GSK
	Proportion of Subjects in DAS28(CRP) Remission at Week 24	N	Y	GSK
ACR response	Predictive Probability of the Difference Over Placebo in the Proportion of Subjects in DAS28(CRP) Remission at Week 24 being > 25%	N	Y	GSK
	Proportion of Subjects with an ACR20/50/70 Response at Each Visit	Y	Y	GSK

 Produced by the unblinded programming team.

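### The Week 24 dose-response fit drops rescued subjects from every arm except 180 mg, which shrinks the fitted drug effect, and no full-sample Week 12 fit is explicitly scheduled

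*SAP*

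**What the plan says.** SAP Table 6 marks the dose-response output for the DAS28(CRP) score as belonging to Week 24. The accompanying text in 4.9.2.2 states: "The Week 24 primary analysis model will be fitted without covariate terms". The Emax and linear models set out in 4.9.2.1 take dose as their only input.

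Three rules determine which values enter that fit:

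- SAP 3.1.3: escape therapy "is provided for all subjects not on the 180 mg dose". The first trigger is failure to reach a EULAR good or moderate response at Week 12, with the higher dose starting at Week 14.
- SAP 4.3.1: continuous results of rescued subjects "will be set to missing at the same visits that were set to non-responder for the binary endpoints".
- SAP 4.5.2.1: subjects who escalate at Week 14 or 26 "should be set to treatment failure at that visit and all subsequent visits (continuous endpoints will be set to missing").

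On Week 12, SAP 4.9.1.1 keeps a hypothesis headed "Dose response relationship (change from baseline in DAS28(CRP) at Week 12"), and protocol 9.4.2 makes Week 12 dose response the key secondary analysis in the ITT population. The only Week 12 fits explicitly listed are among the interim outputs in SAP Table 5: "Dose Response Modelling of Change from Baseline in DAS28(CRP) at Weeks 4, 8 and 12". SAP Table 4 triggers those interims at 90 subjects.

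Multiple imputation is the only stated remedy for missing values in the dose-response model. SAP 4.5.2.3 combines the imputed-data estimates "for use in inference regarding the dose response relationship at Weeks 24 or 52 visits". SAP 4.9.2.2 makes this conditional on a dropout rate of at least 10%, in which case "further sensitivity analyses using multiple imputation as explained in section 4.5.2.3 may be conducted as ad-hoc analyses".

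**The concern.** The rescue rule selects on outcome, and it does so in five of the six arms. At Week 24 the placebo to 135 mg arms have lost their Week 12 non-responders, while the 180 mg arm keeps its own. The steroid and withdrawal rules also remove values, but they apply to all arms alike. Only rescue is asymmetric. Because the model contains neither Week 12 data nor baseline, nothing in it can correct for the selection.

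The trial exists to choose dose(s) for Phase 3. A dose-response curve at the primary timepoint that understates the drug effect because of how rescue is handled is a poor basis for that choice. The raw 180 mg mean is also put at a disadvantage against 135 mg. A Week 12 fit would avoid the problem, but the SAP does not explicitly schedule one in the full sample.

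**Working it through.** **Plan's own figures.** SAP 4.13.2 and protocol 9.2.1.2 give E0 = -1.0, Emax = -1.65 and SD 1. ED50 is not stated; 45 mg reproduces the table. With Y = -1.0 - 1.65 × D/(45 + D):

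- 22.5 mg: -1.0 - 1.65 × 22.5/67.5 = -1.55 (plan -1.54)
- 45 mg: -1.0 - 1.65 × 45/90 = -1.83
- 90 mg: -1.0 - 1.65 × 90/135 = -2.10
- 135 mg: -1.0 - 1.65 × 135/180 = -2.24
- 180 mg: -1.0 - 1.65 × 180/225 = -2.32

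The true 180 mg minus placebo effect is therefore -2.32 + 1.00 = -1.32.

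**Assumptions not in the documents.** The same means hold at Week 24; baseline DAS28(CRP) has mean 5.0 to 6.0 and SD 0.9; the correlation ρ between Week 12 and Week 24 change is 0.3 to 0.9; there is no dropout and no steroid-related blanking.

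**Step 1: who is blanked.** EULAR non-response means improvement of 0.6 or less, or of 1.2 or less with a current score above 5.1. On placebo the first part alone is P(Z > 1.0 - 0.6) = 1 - Φ(0.4) = 34.5%; the second part adds to this. At baseline 5.5, with 35 per arm:

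| Arm | Non-response at Week 12 | Values left at Week 24 |
|---|---|---|
| Placebo | 41.4% | 20.5 |
| 22.5 mg | 22.5% | 27.1 |
| 45 mg | 15.5% | 29.6 |
| 90 mg | 10.0% | 31.5 |
| 135 mg | 7.8% | 32.3 |
| 180 mg | 6.7%, but no rescue | 35 |

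Over baseline means 5.0 to 6.0, blanking is 38-46% on placebo, 20-27% on 22.5 mg, 13-18% on 45 mg, 8-12% on 90 mg, 6-10% on 135 mg and 0% on 180 mg.

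**Step 2: shift in the retained means.** With equal SDs, the retained Week 24 mean is μ + ρk, where k is the retained Week 12 mean minus μ. In simulation at baseline 5.5 the retained placebo mean is -1.32 at ρ = 0.5 and -1.51 at ρ = 0.8. Both give k = -0.32/0.5 = -0.51/0.8 = -0.64. For 135 mg the mean moves from -2.24 to -2.36 at ρ = 0.8, so k = -0.15. For 180 mg k = 0. The raw 180 mg minus placebo difference is then -1.32 + 0.64ρ.

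**Step 3: fitted effect.** Fitting the three-parameter Emax model to the retained values gives:

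| ρ | Raw difference | Fitted, large sample, baseline 5.5 | Shrinkage, baseline 5.0-6.0 | Mean fitted, trials of 35 per arm |
|---|---|---|---|---|
| 0.3 | -1.13 | -1.15 | 12-14% | -1.17 |
| 0.5 | -1.00 | -1.03 | 20-24% | -1.05 |
| 0.7 | -0.87 | -0.92 | 28-34% | -0.94 |
| 0.9 | -0.74 | -0.81 | 37-43% | -0.82 |

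The trial-level standard error is 0.20-0.24, and complete data give a mean of -1.33. If the true effect is half as large (-0.66), shrinkage over the same correlations is 21-24%, 34-40%, 48-55% and 61-70%. With no drug effect and ρ = 0.7, 180 mg would look 0.64 × 0.7 = 0.45 worse than placebo. At ρ = 0 there is no bias.

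**Step 4: order of 135 mg and 180 mg.** The raw 135 mg mean beats the raw 180 mg mean in 36-37% of simulated trials with complete data and in 44-60% after blanking. The fitted curve reversed the two in none.

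**Step 5: alternatives.** Imputing the blanked values from baseline and Week 12 under missing at random gives -1.33 to -1.34 (SE 0.21-0.25). A Week 12 fit gives -1.33 with SE 0.20 at 35 per arm, against SE 0.30 at the interim's 15 per arm.

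**The case against.** The best counter-argument concerns the reading of the SAP. Week 24 is also the name of a delivery in Table 4. SAP 4.9.2.2 promises results for all evaluable endpoints at that delivery and all analyses at the final one. The Week 12 endpoint and hypothesis are kept, and SAP 4.14 does not declare the Week 12 analysis dropped. A full-sample Week 12 fit may therefore be intended. That is possible, and it is why the gap is described only as not explicitly scheduled. But 4.5.2.3 speaks of dose-response inference at the Week 24 or 52 visits, and the SAP uses ITT for the 90-subject interims too, so that label does not settle the sample. If two readings are open, the visit has to be stated.

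The size depends on inputs the documents do not give. That stands, and it is why a range is shown; the direction needs only a positive correlation. The half-effect figures describe a drug that would usually meet the Interim 2 stopping criterion (about 85% of trials simulated at 15 per arm), so they carry less weight. Arms may also be dropped, so six arms of 35 is a simplification.

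Calling this bias assumes the target is the effect had subjects stayed on their randomised dose. The SAP states no target for this fit, but responders in five arms against everyone in the sixth matches no sensible one.

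SAP 3.1.4 refers to a rescue option for all subjects, which should be reconciled with 3.1.3. It does not remove the asymmetry, since a subject on 180 mg cannot escalate to 180 mg.

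Finally, the damage is limited. The planned MMRM uses pre-rescue visits and baseline and is far less exposed. The primary remission analysis with non-responder imputation is unaffected, and the in-trial dose decisions rest on interim fits. All of this is granted, but none of those is the final dose-response model. The optional imputation is not a safeguard either: rescued subjects stay in the study and may not count towards the undefined dropout rate.

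**Conclusion.** The concern holds and should be fixed. The mechanism follows from the SAP's own rules. Relative to the effect had subjects stayed on their randomised dose, the Week 24 fit understates the 180 mg minus placebo difference by about 12-43% under the plan's assumed means, depending on a Week 12 to Week 24 correlation between 0.3 and 0.9 and a baseline mean between 5.0 and 6.0. At middle correlations of 0.5 to 0.7 the loss is 20-34%. These sizes assume that the Week 12 means also apply at Week 24 and that the fit is made to Week 24 visit values. Relying on the interim for Week 12 costs precision (SE 0.30 against 0.20). The fitted curve does not misorder 135 mg and 180 mg; the harm is an understated curve at the primary timepoint.

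**What to change.** - State in SAP 4.9.2.2 and Table 6 which visits the final dose-response models are fitted at.
- Make the main reported fit the Week 12 change from baseline in the full ITT population, as protocol 9.4.2 envisages.
- For Week 24, fit the dose-response model to the MMRM Week 24 least-squares means with their covariance matrix, or to multiply imputed data using baseline and earlier visits. Either should be a pre-specified step that does not depend on a dropout threshold.
- Label the fit to the set-to-missing data as supportive only.
- Optionally, add baseline DAS28(CRP) as a covariate for precision.

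The cost is SAP wording and modest programming, with no new data. The Week 24 fit would then rest on a missing-at-random assumption and have a slightly larger standard error: 0.21-0.25 with imputation, against 0.20 with complete data.
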